Day 1 is the calendar day of first infusion.

Starting on Day 15, patients will begin a taper (reduction) in OCS (per the ATYR1923-C-002 Oral Corticosteroid Taper Guidelines) from their starting dose of 10-25 mg/day of prednisone (or equivalent) to a target dose of 5 mg/day, to be completed on or before Day 50. The OCS dose will be tapered by 5.0 mg/day every 1 to 2 weeks, depending on the starting dose. Smaller incremental titrations to the target dose of 5 mg/day by Day 50 may be implemented per Investigator judgement. Patients will be maintained at the target dose of 5.0 mg/day (or equivalent) through Week 24/End-of-Study (EOS). Optionally, further titrations in the OCS dose to below 5 mg/day may be attempted after the Week 16 visit, if determined by the Investigator to be feasible.

Patients who develop an acute worsening of symptoms or are unable to adhere to the protocol-defined OCS tapering regimen may receive 'rescue' treatment with higher OCS doses as clinically indicated. Upon resolution of symptoms, the Investigator may choose to reinstitute a taper back down to the target maintenance dose of 5 mg/day. Patients

who require rescue treatment following two attempts at tapering to 5 mg/day may remain on a higher stable dose of OCS as determined by the Investigator. Patients who require an increase in OCS dose at any time in the study should continue to receive blinded study drug and followed through to the end of the study. It is planned that 36 patients with pulmonary sarcoidosis will be randomized into one of 3 sequential cohorts, each comprising 12 patients allocated 2:1 (block size of 6) to ATYR1923:Placebo.

Planned Dose Cohorts

The planned dose cohorts are as follows:

Cohort	Dose (mg/kg)	# of Doses	Dosing Frequency	N	Ratio ATYR1923: Placebo
1	1.0	6	Every 4 weeks	12	2:1
2	3.0	6	Every 4 weeks	12	2:1
3	5.0	6	Every 4 weeks	12	2:1

Safety Monitoring

Ongoing review of blinded safety and tolerability data will be performed by the Medical Monitor and a Tyr Pharma personnel.

An independent Data Safety Monitoring Board (DSMB) will perform interim reviews of unblinded safety, tolerability, and immunogenicity data to review and approve dose escalation to the next highest dose cohort (see *Dose Escalation*) and ad hoc as per Sponsor request if a pattern of unexpected, clinically significant trends or changes in other safety assessments is identified through blinded safety data reviews.

Dose Escalation

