For patients with pulmonary sarcoidosis, the primary goal of treatment is to improve the patient's quality of life, while secondarily managing the inflammation that could lead to the development of more permanent fibrosis and impairment of pulmonary function. Currently, the only available therapy, H.P. Acthar[®] Gel, (Mallinckrodt Pharmaceuticals, 2018) for the treatment of sarcoidosis, which was approved in 1952, is not widely used by physicians due to toxicity and cost issues (Baughman et al, 2016). The consensus standard of care is oral corticosteroids (OCS) that act mainly by suppressing inflammatory genes including interferon gamma (IFN- γ) and tumor necrosis factor-alpha (TNF- α), which are important to sarcoid granuloma development (Schutt et al, 2010, Judson et al, 2012). OCS therapy has been shown to stabilize or improve the

disease, although relapse commonly occurs once OCS therapy is tapered or discontinued (Iannuzzi et al, 2007). Current consensus recommends initiating treatment at a daily prednisone equivalent dose of 20 - 40 mg/day for 1 to 3 months, followed by a taper to 5 to 10 mg/day maintenance dose for 1 year (Hunninghake et al, 1999). For patients who subsequently relapse after taper or discontinuation of OCS therapy, the cycle of dosing is repeated.

Long-term corticosteroid use is associated with significant side effects, including substantial weight gain, development of insulin resistance, osteoporosis, and risk of infection. As well, a cohort of sarcoidosis experts published a consensus that a maintenance dose of greater than 10 mg/day for pulmonary sarcoidosis was to be avoided, when possible (Hunninghake et al, 1999), forming the need for steroid-sparing treatments. Yet, unremitting inflammation may progress into pulmonary fibrosis and death. Alternatives, such as immunosuppressive and cytotoxic agents (eg, methotrexate and TNF-α inhibitors) have been used; however, these therapies can also have significant side effects and toxicities. (Judson et al, 2012). Most published data on the use of these therapies is anecdotal and based on small numbers of patients and results have been variable. Infliximab (TNF-α inhibitor) was shown to improve lung function in those with chronic pulmonary sarcoidosis; however, the treatment effect was modest (Baughman et al, 2006).

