7.1.6.3. Rescue Treatment with Oral Corticosteroids

Patients who develop an acute worsening of symptoms or are unable to adhere to the protocol-defined OCS tapering regimen may receive 'rescue' treatment with higher OCS doses as clinically indicated.

The following criteria should be met prior to providing rescue OCS treatment:

1a) Worsening cough, documented by a decrease of ≥ 1 point on the LCQ,

OR

1b) Worsening dyspnea, documented by an increase of ≥1 point on the TDI,

AND

2) The Investigator's clinical judgement that rescue therapy is warranted.

Rescue therapy is not mandated in the event of worsening cough or worsening dyspnea if the Investigator determines that an increase in steroid dose is not clinically indicated.

Upon resolution of symptoms, the Investigator may choose to reinstitute a taper back down to the target maintenance dose of 5 mg/day.

Patients who require rescue treatment following 2 attempts at tapering to 5 mg/day may remain on a higher stable dose of OCS as determined by the Investigator.

Patients who require an increase in OCS dose at any time in the study should continue to receive blinded study drug and followed through to the end of the study.

Patient will document OCS doses in a diary, which will be reviewed at relevant scheduled telephone contacts and study visits.

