10.1.4. Study Drug Adjusted OCS Burden

Since a missed dose in study treatment is likely to affect OCS dose, in order to isolate the effect of treatment, the above mentioned OCS dose, change from baseline and percent change from baseline analyses will be repeated, but excluding a window around a missed dose of study treatment, where a window is defined as 30 days after the previous dose and restart on the day of the next administered dose. Active treatment and placebo will be compared in the same way as in time adjusted OCS burden in the previous section.

10.1.5. Achievement of Target Taper Dose of Prednisone 5 mg/day (or Equivalent) and Maintained Through Week 24

The number and percentage of patients who have achieved the following will be summarized.

1. **Ability to Taper:** Taper OCS dose level down to 5mg/day or less at any time and remained for at least 5 consecutive days.
2. **Maintain Taper:**
 - a. Taper OCS dose level down to 5mg/day or less at any time and remained for at least 30 consecutive days.
 - b. Taper OCS dose level down to 5mg/day or less at any time and remained for at least 60 consecutive days.
 - c. Taper OCS dose level down to 5mg/day or less at any time and remained for at least 90 consecutive days.
 - d. Taper OCS dose level down to 5mg/day or less at any time and remained for at least 115 consecutive days

- e. Time to first relapse of taper for sarcoidosis. Defined as the duration from the first day of hitting 5mg (plus 5 consecutive days) to when >5mg is needed. If the reason for increase in OCS is unrelated to sarcoidosis (as identified from the eCRF) then that episode will not count as a relapse and counting of the duration will recommence on the next day on which 5mg is achieved. For patients who maintain 5mg after successful taper will be censored at 30 days after last dose or EOS (if earlier). Patients who never reach 5 mg will be assigned a duration of 1 day and be classified as a censored data point.
- f. Proportion of days at 5mg or less ignoring diary days when OCS dose was increased >5mg for non-sarcoidosis events (i.e. same exclusion as the Time to First Relapse endpoint)
- g. Proportion of days at 5mg or less including all diary days (i.e. even those when OCS dose was increased >5mg for non-sarcoidosis events)

In each of the above endpoints, when study drug dosing is missed, OCS diary data >30 days after previous study drug infusion will be ignored until dosing restarted as described in Section 10.1.4.

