11.1.1.1. Mixed Model Repeated Measures Analysis (MMRM)

The absolute values specific parameters specified in Table 2 will be analyzed using a mixed linear model. Treatment and baseline are included as fixed effects. Repeated effect is included for visit. Restricted maximum likelihood method and Kenward and Roger (1997) method for degrees-of-freedom will be used. If a subject's baseline value is missing for a given parameter, then the subject is removed from that parameter's analysis.

This same analysis will be performed with and without multiple imputation as described in Section 7.3.3.5 Each individual/combined active arm will be compared with combined placebo arm.

Unstructured covariance structure will be used, but if convergence is not achieved, then compound symmetry (type=cs) covariance structure will be used.

The following pseudo code will be used.

```
proc mixed data = imputed method=reml;
  by _imputation_;
  class trt01p(ref='Placebo') avisit usubjid;
  model FEV1PP = trt01p avisit trt01p*avisit base / ddfm=kr;
  repeated / subject=usubjid type=un;
  lsmeans trt01p*avisit /pdiff=all cl;
  ods output diffs=lsmdiffl;
run;

proc mianalyze parms(classvar=full)=lsmdiffl;
  class trt01p _trt01p avisit _avisit;
  modeleffects trt01p*avisit;
  ods output ParameterEstimates=lsmdiffEstimate;
run;
```

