11.1.1.2. Random Coefficient Regression Model (RCRM)

Table 2 lists key variables that will also be analyzed in RCRM. This model will include treatment, baseline value and treatment-by-time interaction as fixed effects. Both intercept and continuous time in days are included as random effects. Unstructured covariance structures will be used for slope and intercept. If convergence is not achieved, then compound symmetry covariance structure (type=cs) is used and/or the random intercept may be removed. Restricted maximum likelihood and Kenward Rogers (1997) method for degrees-of-freedom will be used.

This same analysis will be performed with and without multiple imputation as described in Section 7.3.3.5. Each individual/combined active arm will be compared with combined placebo arm.

aTyr Pharma, Inc.
 Study ATYR1923-C-002 Statistical Analysis Plan
 IND#: 133692

FINAL Version 1.0
 2021-08-02

Pseudo code below will be used.

For comparing individual arms with placebo:

```
proc mixed data=imputed method=reml;
  class TRT01P(ref='Placebo') usubjid;
  by _imputation_;
  model &pftparm.=TRT01P BASE TRT01P*ady/noint solution ddfm=kr;
  random intercept ady/subject=usubjid type=un; *unstructured covariance
  structure had half of the trials not converge;
  estimate 'A_V_P' TRT01P*ady 1 0 0 -1/ CL;
  estimate 'B_V_P' TRT01P*ady 0 1 0 -1/ CL;
  estimate 'C_V_P' TRT01P*ady 0 0 1 -1/ CL;
  estimate 'T_V_P' TRT01P*ady 1 1 1 -3/ CL divisor=3;
  ods output Estimates=ran_coef_est(rename=(label=effect));
run;

proc mianalyze parms(classvar=full)=ran_coef_est;
  *class A_V_P B_V_P C_V_P A_V_B B_V_C A_V_C;
  modeleffects A_V_P B_V_P C_V_P A_V_B B_V_C A_V_C;
  ods output ParameterEstimates=rcrm_est;
run;
```

For combined active vs. placebo:

```
proc mixed data=imputed method=reml;
  class TRT01P(ref='Placebo') usubjid;
  by _imputation_;
  model &pftparm.=TRT01P BASE TRT01P*ady/noint solution ddfm=kr;
  random intercept ady/subject=usubjid type=un; *unstructured covariance
  structure had half of the trials not converge;
  estimate 'A_V_P' TRT01P*ady 1 0 0 -1/ CL;
  ods output Estimates=ran_coef_est(rename=(label=effect));
run;

proc mianalyze parms(classvar=full)=ran_coef_est;
  class A_V_P;
  modeleffects A_V_P;
  ods output ParameterEstimates=rcrm_est;
run;
```

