11.1.3. Health-Related Quality of Life

Health-Related Quality of Life, as assessed by the SAT, SAC BDI-TDI, KSQ, LCQ, and FAS. Scores and change from baseline for each questionnaire are summarized and listed using the mITT and EE Set.

For the change from baseline for each subscore or total score below, individual/combined active treatment arm will be compared to placebo using the pseudo code below. The integer scores are treated as continuous. Restricted maximum likelihood and Kenward Rogers (1997) method for degrees-of-freedom will be used.

```
proc mixed data = score method=reml;
  class trt01p(ref='Placebo') avisit usubjid;
  model change_from_baseline = trt01p avisit trt01p*avisit base / ddfm=kr;
  repeated / subject=usubjid type=un;
  lsmeans trt01p*avisit /pdiff=all cl;
run;
```

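### Lung function, quality-of-life and PET values taken after rescue steroid are analysed with no allowance for rescue, so treatment differences on these exploratory endpoints can be diluted

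*Protocol*

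**What the plan says.** **Rescue.** The protocol (Synopsis; 4.1; 7.1.6.2) tapers every patient from 10-25 mg/day to 5 mg/day between Day 15 and Day 50. Patients who worsen may have the dose raised, and follow-up goes on: "Patients who require an increase in OCS dose at any time in the study should continue to receive blinded study drug". Protocol 7.1.6.3 asks for documented worsening first. One route is "Worsening cough, documented by a decrease of ≥ 1 point on the LCQ"; the other is a change on the TDI; both also need the Investigator's judgement. LCQ and TDI are themselves exploratory endpoints (SAP 4.2.3).

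**Clinical analyses.** For the lung-function MMRM, SAP 11.1.1.1 states "Treatment and baseline are included as fixed effects. Repeated effect is included for visit", and its code adds the treatment-by-visit interaction. For the random coefficient model, SAP 11.1.1.2 states "This model will include treatment, baseline value and treatment-by-time interaction as fixed effects". The quality-of-life model in SAP 11.1.3 is "model change_from_baseline = trt01p avisit trt01p*avisit base / ddfm=kr". SAP 11.1.2 takes the change in regional SUVmax from screening to Week 16.

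**Steroid analyses.** Here the SAP does separate causes of a dose rise. Item 2e of SAP 10.1.5 begins its exception with "If the reason for increase in OCS is unrelated to sarcoidosis (as identified from the eCRF" and does not count such an episode as a relapse.

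**The concern.** Rescue is triggered by outcome, and steroid acts on the same disease: Protocol 2.1 says that "OCS therapy has been shown to stabilize or improve the" disease, and that relapse is common once steroid is tapered. If the drug prevents relapse, the placebo arm receives more rescue, and its later FVC, LCQ, TDI and SUVmax values may be pulled back towards baseline. The planned models then compare drug against placebo plus extra steroid. That is a legitimate question, but the SAP does not say it is the one intended, and it offers no contrast.

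At stake is the exploratory objective, preliminary efficacy on lung function, symptoms and disease activity. Weeks 16 and 24, two of the main lung-function time points (SAP 11.1.1), and the Week 16 scan all fall after the taper, when rescue may already have acted. The Worsening endpoint (two consecutive falls of more than 5%) is exposed too, because rescue between visits can prevent the second low value.

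**Working it through.** **Step 1. Is there a rescue provision anywhere in the clinical analyses?**
- MMRM, random coefficient and quality-of-life models (SAP 11.1.1.1, 11.1.1.2, 11.1.3): no OCS or rescue term.
- PET (11.1.2): no rule for OCS dose at the scan.
- Multiple imputation (7.3.3.5): fills missing lung-function values from other visits, post-rescue ones included.
- EE Set (7.1.3): at least four doses and no major deviation. Permitted rescue is not a named exclusion.
- Exclusion window for missed study drug (10.1.4, 10.1.5): steroid endpoints only.

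None exists. The inputs do: daily OCS dose (SAP 10.1.1) and the reason for an increase (10.1.5, item 2e).

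**Step 2. How much could be lost?** The plan states no effect size, SD, rescue rate or power, so there is no figure to reproduce. A simple model is

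observed difference = e + (p0 − p1) × L × (1 − r)

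where e is drug effect not acting through relapse, p0 and p1 are the placebo and active relapse rates (relapsers are rescued), L is a relapser's loss if not rescued, and r is the share of that loss restored by steroid. All values are assumed, with L = 10 points of percent-predicted FVC.

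| p0, p1 | e | No rescue (r = 0) | r = 0.5 | r = 1 |
|---|---|---|---|---|
| 0.60, 0.30 | 0 | 0.30 × 10 = 3.0 | 1.5 | 0 |
| 0.60, 0.30 | 2 | 5.0 | 3.5 | 2.0 |
| 0.40, 0.30 | 2 | 3.0 | 2.5 | 2.0 |
| 0.40, 0.40 | 2 | 2.0 | 2.0 | 2.0 |

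Taking placebo relapse as 40-60%, active 20-30%, L as 5-10 and e = 0, the difference without rescue runs from (0.4 − 0.3) × 5 = 0.5 to (0.6 − 0.2) × 10 = 4.0 points. With r from 0.5 to 1, the observed difference runs from 0 to 2.0.

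**Step 3. Precision.** For 24 active against 12 placebo, the standard error is √(1/24 + 1/12) = 0.354 SD, so the difference detectable with 80% power at two-sided 0.05 (an illustrative level) is (1.96 + 0.84) × 0.354 = 0.99 SD. For one dose (8 against 12) it is 1.28 SD. With an assumed SD of 6 points, power in the first row of the table is 0.29 without rescue and 0.11 at r = 0.5. In the second row it is 0.65, 0.38 and 0.15.

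**Step 4. Would setting post-rescue values to missing recover the difference?** Assume relapse in 60% and 30%, a fall of 10, and a true Week 24 difference of 3.0.
- *Fall recorded at a visit before rescue*, first seen evenly over the five visits from Week 8 to Week 24. The all-data difference is 3.0 × (1/5 + 4/5 × (1 − r)), which is 1.8 at r = 0.5 and 0.6 at r = 1. Large-sample simulation of the filtered model gives about 2.1 to 2.5, depending on the assumed visit-to-visit variation.
- *Fall and rescue both between visits.* The all-data difference is 3.0 × (1 − r), which is 1.5 to 0. The filtered model gives about 0.
- *Placebo Week 24 values kept:* 0.40 + 0.60/5 = 52% in the first case and 40% in the second, or about 6.2 and 4.8 of 12 patients.

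The filter helps where the worsening is captured before rescue, and can do worse than the all-data model where it is not.

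**The case against.** The strongest reply is that nothing here is broken. Following rescued patients on blinded drug is what an all-data, treatment-policy comparison needs. The endpoints are exploratory in a 36-patient safety trial with no formal hypothesis testing (SAP 7.4.1), no multiplicity adjustment (7.5) and no power calculation (6); PET is optional. In the first row of the table, power is only 0.29 before any dilution. All of that stands, and it limits the weight of the point.

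A reader might infer three stronger things that the documents do not support.
- *That a real benefit will be hidden.* This needs unequal rescue rates, an effect acting only through relapse, and near-full recovery on steroid. None is given. FVC is not a rescue criterion, so even the assumed FVC fall in relapsers is a supposition.
- *That a flat result could not be told apart from no effect.* Within the trial it largely could. OCS burden, taper maintenance, time to first relapse, days at 5 mg or less and dose-time profiles (SAP 10.1.3 to 10.1.6) would show a relapse benefit. Flat FVC with lower OCS use differs from flat FVC with equal use.
- *That placebo patients reach Week 24 on more steroid.* The protocol allows a second taper once symptoms resolve.

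What remains is that the steroid endpoints alone do not show whether a flat FVC, LCQ or SUVmax result reflects no effect on that measure or rescue acting on it.

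**Conclusion.** The concern holds in a limited form. The SAP analyses lung function, quality of life and SUVmax after rescue with no stated strategy and no contrast, although it separates sarcoidosis-related OCS increases for the steroid endpoints. If the drug reduces relapse, the expected bias is towards no difference. The relapse-mediated part of an effect shrinks by exactly the share that steroid restores; a direct effect is not reduced; equal rescue rates give no dilution. The true size cannot be fixed from the documents, and every figure above rests on assumed rates, losses and recovery. The primary safety and secondary steroid analyses are unaffected. This is a cheap improvement to interpretation, not a flaw in the design.

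**What to change.** Change the SAP only, before unblinding, and keep the all-data models, named as the treatment-policy analysis.

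1. **Describe rescue.** Tabulate by arm and visit the OCS dose and whether a sarcoidosis-related OCS increase has occurred at each lung-function, quality-of-life and PET assessment. In 11.1.2, flag patients rescued before the Week 16 scan.
2. **One supplementary run, one rule.** Rerun the 11.1.1.1, 11.1.1.2 and 11.1.3 models with values set to missing after the first sarcoidosis-related OCS increase recorded on the eCRF. Keep the value that documented the worsening before rescue. Report values removed per arm. State that the rule applies to any such increase on study, since item 2e counts only after 5 mg has been reached.
3. **Cover the case the filter misses.** Add a supplementary version of the Worsening endpoint that counts a sarcoidosis-related OCS increase as an event.

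The cost is a filter on existing code, some tables and no new data. The downside is a missing-at-random assumption and fewer late values: 40-52% of placebo Week 24 values kept if 60% relapse, an assumed rate. Too few values may also push the unstructured covariance to the SAP's compound-symmetry fallback.

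Separately, Protocol 7.1.6.3 documents worsening dyspnoea by a rise in TDI, while Protocol 8.2.5.2 and SAP 11.1.3.2 say a lower TDI means deterioration. These passages must be reconciled, since the TDI is both a rescue criterion and an endpoint.

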2. INTRODUCTION

2.1. Pulmonary Sarcoidosis

Pulmonary sarcoidosis is a form of interstitial lung disease (ILD) in which immune cells play a predominant role. Chronic hypersensitivity pneumonitis (CHP), polymyositis/dermatomyositis ILD (PM/DM-ILD), and connective tissue disease associated ILD (rheumatoid arthritis ILD; systemic sclerosis-associated ILD) are examples of other immune-mediate ILDs. These lung conditions are recognized as having a measurable immune component involving both innate and adaptive immune mechanisms that contribute to pathogenesis at several cellular and non-cellular levels (Kolahian et al, 2016; Meyer et al, 2014).

Sarcoidosis is a multisystem granulomatous disorder of unknown etiology that is characterized pathologically by the presence of non-caseating granulomas (Hunninghake et al, 1999). Sarcoidosis frequently presents with bilateral hilar lymphadenopathy, pulmonary infiltration, and ocular and skin lesions. This disease affects people of all ages, but typically presents before the age of 50 years, with the incidence peaking at 20-39 years (Iannuzzi et al, 2007). The lungs are affected in more than 90% of patients with sarcoidosis (Baughman et al, 2011). Although spontaneous remissions occur, chronic or progressive disease is seen in 10–30% and the disease is fatal in 15% of patients, typically due to progressive respiratory insufficiency, central nervous system, or myocardial involvement. The liver, spleen, lymph nodes, salivary glands, heart, nervous system, muscles, bones, and other organs may also be involved. While sarcoidosis most frequently involves the lungs and thoracic lymph nodes, up to 30 percent of patients present with extrathoracic manifestations of sarcoidosis.

In the lung, granulomas are most commonly found in the alveolar septa, the walls of bronchi, the pulmonary arteries and veins. The sarcoid granuloma is characterized by a core of monocyte-derived epithelioid histiocytes and multinucleate giant cells with interspersed CD4+ T lymphocytes (Baughman et al, 2011). A minority of cells in or near the granuloma are CD8+ lymphocytes, fibroblasts, regulatory T-cells, and B lymphocytes.

For patients with pulmonary sarcoidosis, the primary goal of treatment is to improve the patient's quality of life, while secondarily managing the inflammation that could lead to the development of more permanent fibrosis and impairment of pulmonary function. Currently, the only available therapy, H.P. Acthar[®] Gel, (Mallinckrodt Pharmaceuticals, 2018) for the treatment of sarcoidosis, which was approved in 1952, is not widely used by physicians due to toxicity and cost issues (Baughman et al, 2016). The consensus standard of care is oral corticosteroids (OCS) that act mainly by suppressing inflammatory genes including interferon gamma (IFN- γ) and tumor necrosis factor-alpha (TNF- α), which are important to sarcoid granuloma development (Schutt et al, 2010, Judson et al, 2012). OCS therapy has been shown to stabilize or improve the

disease, although relapse commonly occurs once OCS therapy is tapered or discontinued (Iannuzzi et al, 2007). Current consensus recommends initiating treatment at a daily prednisone equivalent dose of 20 - 40 mg/day for 1 to 3 months, followed by a taper to 5 to 10 mg/day maintenance dose for 1 year (Hunninghake et al, 1999). For patients who subsequently relapse after taper or discontinuation of OCS therapy, the cycle of dosing is repeated.

Long-term corticosteroid use is associated with significant side effects, including substantial weight gain, development of insulin resistance, osteoporosis, and risk of infection. As well, a cohort of sarcoidosis experts published a consensus that a maintenance dose of greater than 10 mg/day for pulmonary sarcoidosis was to be avoided, when possible (Hunninghake et al, 1999), forming the need for steroid-sparing treatments. Yet, unremitting inflammation may progress into pulmonary fibrosis and death. Alternatives, such as immunosuppressive and cytotoxic agents (eg, methotrexate and TNF-α inhibitors) have been used; however, these therapies can also have significant side effects and toxicities. (Judson et al, 2012). Most published data on the use of these therapies is anecdotal and based on small numbers of patients and results have been variable. Infliximab (TNF-α inhibitor) was shown to improve lung function in those with chronic pulmonary sarcoidosis; however, the treatment effect was modest (Baughman et al, 2006).

Given the known toxicities of long-term corticosteroids, immunosuppressives and cytotoxic therapeutic regimens, treatment of patients with sarcoidosis is limited to those who are symptomatic and whose disease is considered 'active'. The presence of granulomas from sarcoidosis define the disease as active (Beegle et al, 2013), and granulomatous inflammation is the major cause of fibrosis in pulmonary sarcoidosis. Studies to date have not clearly demonstrated that corticosteroids or other immunosuppressive therapy prevents disease progression or formation of fibrosis (Baughman et al, 2011). Therefore, there exists a substantial need for safer and more effective therapies for sarcoidosis.

